16. STUDY MEDICATION COMPLIANCE

Total number of tablets expected, total number of tablets taken, total number of tablets missed, overall compliance to study treatment, frequency and percentage of subjects with overall compliance of <80% or >120% are based on Dosing Administration in the EDC. They will be summarized for the Safety Set for both the Double-Blind Period and Extension Period.

16.1. DERIVATIONS

Compliance to study treatment is based on the Drug Accountability eCRF and will be calculated as the number of tablets taken (total dispensed – total returned) divided by the prescribed number of tablets expected during the treatment period, expressed as a percentage, see calculations below.

The total number of tablets expected is defined as the number of tablets that a subject is expected to have taken between their first and last study treatment administration and is numerically identical to the subject's overall study treatment exposure, since the medication is to be taken once daily. On any site visit day, the medication is to be held and taken at the site, after all predose assessments have been completed. For example, if a subject took their last dose of study treatment on Day 60 and returned to the site on Day 78 to return the study treatment bottle, then the total number of tablets expected would be 60, not 77.

- Overall Compliance to study treatment will be calculated as follows:

$$\frac{([\text{Total N of tablets dispensed in the study}] - [\text{Total N of tablets returned in the study}])}{[\text{Date of last dose}] - [\text{Date of first dose}] + 1} \times 100$$

If a bottle is not returned, all dispensed tablets will be assumed to be taken. For each subject, if a high percentage (> 25%) of bottles were not returned by a subject, additional analyses may be done where bottles not returned are excluded from the overall compliance calculation for the subject. In such analysis, the date of last dose or the date of last bottle return, whichever is earlier, will be used as the “date of last dose” in the calculation above.

Both scheduled and unscheduled study treatment dispensations will be used in the compliance calculation. Overall

compliance calculations will be performed for the Double-Blind Treatment Period and the entire study and will be used in determining inclusion/exclusion of subjects in the Per Protocol Set. For subjects discontinued prior to Week 16, their overall compliance for the 16 Week Treatment Period and the entire study will be identical. For subjects who remained in the study beyond Week 16, the 16 Week total tablets expected will be defined as Date of Week 16 visit – Date of first dose, since their last dose in the 16 Week Treatment Period should have been taken on the day before Week 16 visit.

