7.4. Accountability

Subjects will be instructed to record tablet self-administration daily and to document the time of their last dose prior to each study visit in an electronic diary (eDiary) that will be reviewed at each study visit by study site staff.

At each site visit, subjects will return all dispensed medication bottles and any remaining tablets to study site staff; remaining tablets will be collected and counted by the Investigator or qualified staff to confirm subject compliance. The number of remaining tablets in the bottle may be counted by visual inspection via videoconferencing for virtual assessment. In this scenario, all bottles and any remaining tablets must be returned at the next study site visit.

The Investigator must maintain adequate records documenting the receipt, use, loss, or other disposition of study treatment tablets. To ensure adequate records, all drug supplies will be accounted for in the drug accountability inventory and will be monitored by counting of unused study treatment tablets.

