5.5. PER PROTOCOL SET

The Per Protocol Set will consist of all subjects in the FAS without major protocol violations on or before Week 16 that might affect the evaluation of the effect of study treatment on the primary endpoint. This set will be used in sensitivity analyses of the primary and secondary endpoints to evaluate the influences of major protocol violators and deviators on the primary results. Subjects will be excluded from the Per Protocol Set if they violate the eligibility criteria or significantly deviate from the study plan, including:

- Study treatment non-compliance (< 80 or > 120%)
- Received incorrect study treatment for > 7 days in total
- Used rescue medication or undergo rescue medical procedure that may affect primary efficacy endpoint at Week 16
- Missed Week 16 esophageal PEC in pre-specified analysis window per Section 6.4 for reasons other than discontinuing due to lack of efficacy

All protocol deviations will be reviewed in addition to the programmable deviations listed above (e.g., study treatment non-compliance) to determine if any deviation is significant enough to exclude a subject from the Per Protocol Set. All exclusion flags will be finalized before study unblinding. Subjects excluded from the Per Protocol Set will be listed along with the reason category above. Subjects will be summarized by treatment to which they were randomized, regardless of treatment actually received.

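### SAP 16.1 counts an unreturned bottle as fully taken while expected tablets stop at the last dose, so the compliance limits can wrongly drop some early stoppers from the Per Protocol Set and keep some non-compliers

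*SAP*

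**What the plan says.** SAP 16.1 defines overall compliance as tablets dispensed minus tablets returned, divided by the days from first to last dose inclusive. The expected count "is numerically identical to the subject's overall study treatment exposure, since the medication is to be taken once daily". In the SAP's example, the last dose is on Day 60 and the bottle comes back on Day 78; "then the total number of tablets expected would be 60, not 77". For missing bottles the rule is "If a bottle is not returned, all dispensed tablets will be assumed to be taken". If more than 25% of a subject's bottles are missing, a further analysis leaving those bottles out is optional.

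SAP 16.1 says that compliance for the Double-Blind Treatment Period and for the entire study feeds Per Protocol membership, then goes on to describe a 16-week version. SAP 5.5 limits the relevant violations to Week 16 or earlier and excludes compliance below 80% or above 120%. It also excludes subjects with no Week 16 PEC in the analysis window, but only "for reasons other than discontinuing due to lack of efficacy".

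The data source is stated twice and differently. SAP 16 says that the compliance summaries "are based on Dosing Administration in the EDC"; SAP 16.1 says "Compliance to study treatment is based on the Drug Accountability eCRF". Protocol 7.4 provides a separate record: "Subjects will be instructed to record tablet self-administration daily".

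**The concern.** The numerator can include tablets for which the denominator allows no days. A subject who took one tablet a day, stopped early and did not return the bottle then looks like an over-user and fails the 120% limit. The opposite error arises when a bottle is lost unused in mid-study: its tablets fill the gap and hide the missed doses.

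The Per Protocol analyses of the primary and secondary endpoints exist to show how far protocol violators influence the results. If membership depends on whether a bottle came back, they do this less well. With about 96 subjects randomized 3:3:2, placebo has about 96 × 2/8 = 24 subjects and each etrasimod arm 36, so one misclassified subject is about 4% or 3% of an arm.

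**Working it through.** **Inputs.** The formula, the unreturned-bottle rule and the 25% option are from SAP 16.1; the 80% and 120% limits and the missed-PEC rule from SAP 5.5; the Week 16 window (Days 100 to 127) from SAP 6.4. Dispensing at Day 1, Week 8 and Week 16 is from protocol Table 7, and the Early Termination visit within 7 days of last dose from protocol 9.6. Tablets per bottle are not stated. I assume 56 per 8-week supply and show a range of 56 to 70, or 28 to 35 if only one 4-week bottle is unreturned.

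**The SAP's own figure.** Expected tablets = 60 − 1 + 1 = 60; the rejected figure is 78 − 1 = 77. Both reproduce. If the Week 8 supply in that example were never returned, compliance would be (56 + 56)/60 = 187%.

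**Early stop, current supply not returned.** Earlier supplies are taken as used once daily, with any surplus returned; the current one is counted in full.

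- First supply: 56/t > 1.2 when t < 46.7, so last dose on Days 1 to 46 (46 days).
- Second supply: 112/t > 1.2 when t < 93.3, so Days 57 to 93 (37 days).
- Before Week 16: 46 + 37 = 83 of 112 days (74%).
- Third supply: 168/t > 1.2 when t < 140, so Days 113 to 139 (27 of 56 days).

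Last-dose days scoring above 120%, by number of unreturned tablets assumed:

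| Unreturned supply | Days 1–112 | Days 94–112 | Days 113–168 |
|---|---|---|---|
| 56 per 8 weeks | 83 (74%) | 0 of 19 | 27 of 56 |
| 60 per 8 weeks | 89 (79%) | 3 of 19 | 31 of 56 |
| 70 per 8 weeks | 104 (93%) | 11 of 19 | 39 of 56 |
| 28 per 4 weeks | 63 (56%) | 0 of 19 | 4 of 56 |
| 35 per 4 weeks | 86 (77%) | 6 of 19 | 15 of 56 |

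**Who is newly excluded.** An Early Termination endoscopy within 7 days reaches Day 100 only if the last dose is on Day 93 or later (93 + 7 = 100). Earlier stoppers generally leave under the missed-PEC rule whatever their compliance, unless they stopped for lack of efficacy. At 56 tablets, Day 93 gives 112/93 = 120.4%, and no day from 94 to 112 exceeds 120%. A subject who stops on Days 113 to 139 can have a valid Week 16 PEC and 16-week compliance of 112/112 = 100%, yet exceed 120% if the 24-week figure is used.

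**Bottle lost with nothing taken from it.**

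- Week 8 supply, subject stays past Week 16: (56 + 56)/112 = 100% over 16 weeks, against a true 56/112 = 50%. Over 24 weeks, 168/168 = 100% against 112/168 = 66.7%. Both true values are below 80%.
- Final supply, dosing ended on Day 56: (56 + 56)/56 = 200%, so the subject is excluded, not kept.

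**The SAP's optional calculation.** With the Week 8 supply unreturned, last return on Day 57 and last dose on Day 80, the main rule gives 112/80 = 140% and the option 56/57 = 98.2%. With one bottle per dispensing, one missing bottle (1/1, 1/2 or 1/3) always passes the 25% trigger. With two per dispensing it can fail (1/4 = 25%, 1/6 = 17%). If the only bottle dispensed is missing, the option has no tablets and no return date.

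**The case against.** The strongest reply is that the problem is small and partly foreseen. Protocol 7.4 requires all bottles back at each site visit, accountability is scheduled at Early Termination, and subjects who return bottles get a correct figure. No non-return rate is given. The missed-PEC rule already removes most non-lack-of-efficacy subjects who stop before Week 16. Eight weeks without drug would probably be noticed: doses go in a daily eDiary, a gap of 7 or more days requires contact with the site (protocol 6.3.1), and interruptions are recorded on the dosing eCRF (SAP 15). Deviations are reviewed before unblinding, and the SAP already describes a calculation without missing bottles.

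Most of this stands and limits the scope, but it does not repair the rule. The alternative calculation is optional, is not said to govern Per Protocol membership, and is undefined when nothing was returned. The deviation review in SAP 5.5 looks for further subjects to exclude. SAP 5.1 allows changes to the sets but gives no rule for this case. The eDiary and dosing records do not enter the SAP 16.1 formula.

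A reader might also infer that the rule removes treatment failures, and more of them on placebo. The documents do not support this. It reaches only lack-of-efficacy stoppers who also kept the bottle and stopped on certain days, and nothing shows a difference by arm. Under SAP 17.1.2 and 17.1.3 these subjects have missing PEC at later timepoints, imputed within treatment group. Dropping them therefore removes no observed failing Week 16 value from the percent-change analysis. The responder endpoints, where missing counts as nonresponse, are more directly exposed.

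**Conclusion.** The point holds in limited form. Followed as written, SAP 16.1 gives wrong compliance in both directions. Wrong exclusions are mainly of lack-of-efficacy stoppers with an unreturned supply and, if 24-week compliance governs, of subjects who stop soon after Week 16 (Days 113 to 139 at 56 tablets). Wrong retention concerns a mid-study supply lost unused by a subject who stays past Week 16.

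Two wider readings should be resisted. It is not true that most early stoppers score above 120%: the 74% (range 56% to 93%) is a share of possible stop days among those who do not return the supply, and it rests on an assumed pack size. Nor does a lost bottle always look like full compliance; a lost final supply gives about 200%.

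The primary analysis uses the Full Analysis Set and is unaffected. The conflict between SAP 16 and 16.1 over the source, and the unclear compliance period, need correcting whatever the pack size, since the reported compliance and the Per Protocol flag could differ for the same subject.

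**What to change.** In SAP 16.1, make the following mandatory for Per Protocol membership:

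- For any unreturned bottle, take tablets used from the Dosing Administration record or the daily eDiary (protocol 7.4).
- If neither exists, remove that bottle and the days it covers from both numerator and denominator.
- Define the outcome when no bottle was returned and no dosing record exists, for example as not evaluable with a stated in-or-out rule.
- State that Per Protocol compliance covers Day 1 to Week 16, in line with SAP 5.5.
- Name one data source in both SAP 16 and SAP 16.1.

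The cost is SAP wording and a small derivation change using data already collected. The drawback is that eDiary and dosing entries are partly self-reported, so they may overstate intake.

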17. EFFICACY OUTCOMES

17.1. PRIMARY EFFICACY

17.1.1. PRIMARY EFFICACY VARIABLE & DERIVATION

The primary efficacy variable is percent change from Baseline in esophageal PEC at Week 16. Esophageal PEC will be based on the central esophagogastroduodenoscopy (EGD) results. A decrease in esophageal PEC indicates improvement in disease.

17.1.2. MISSING DATA METHODS FOR PRIMARY EFFICACY VARIABLE

Subjects who 1) discontinue the study for worsening of disease, lack of efficacy, or adverse event related to EoE, 2) use a rescue medication for EoE, or 3) have rescue medical procedure during the study as confirmed after blinded review by clinical and medical team members before study unblinding will be considered to have a missing outcome in the analysis of all efficacy endpoints at any subsequent timepoints, including the primary endpoint. The rescue medications/rescue medical procedure will be identified by the Pfizer clinical team during blinded data review. The detailed information regarding the identification of rescue therapy is provided in Appendix 4. In scenarios 2 and 3 above, if a subject has an efficacy measurement collected after the initiation of rescue medication/rescue medical procedure, the observed data will be censored at the time of initiation and they will be considered as having a missing outcome. Subjects in all 3 scenarios above may still be included in the respective Per Protocol Set, provided they do not violate other criteria for Per Protocol Set. For example, they will be excluded from the respective Per Protocol Set if they initiate a prohibited medication before the Week 16 efficacy assessment that can affect efficacy of the study treatment and the indication is unrelated to EoE.

Analysis visits will be mapped as per Section 6.4 before any missing data imputation method is applied.

Subjects who initiate rescue medication will have PEC results after the start of rescue medication/rescue medical procedure set to missing. All missing PEC at Week 16 and Week 24 will then be imputed using multiple imputation under missing at random (MAR) procedure with a fully conditional specification (FCS) and predictive mean

matching for PEC as the primary missing data method. There are two different types of missing data patterns: non-monotone and monotone. A subject with missing data at any post-Baseline visit, and a non-missing data point after that visit is said to have intermittent missing data (non-monotone). A subject with missing data at any post-Baseline visit and at all subsequent visits is said to have monotone missing data.

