9.6. Early Termination

Subjects who discontinue the study prior to the end of the 24-week Double-Blind Treatment Period or the 28-week Extension Treatment Period (Week 52) will return to the study site for an ET Visit. The ET Visit should occur within 7 days of last dose and before initiation of any new treatments.

Site staff will work with subjects who withdraw early to obtain as much follow-up data as possible, including an EGD, if not done within 4 weeks, and PFTs and ophthalmic and OCT testing. If a subject discontinues due to pregnancy, they may not be required to complete the EGD and biopsy.

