11.4. Missing Data

11.4.1. Primary Methods of Handling Missing Data and Rescue Medication/Rescue Procedure Usage

In order to analyze efficacy endpoints at Week 16 and Week 24 in the Full Analysis Set (FAS), handling missing data and rescue medication uses are specified as following. For the endpoint of the percent change from Baseline in esophageal PEC at Week 16 and Week 24, PEC after rescue medication/rescue procedure use will be set to missing. All missing PEC at scheduled visits up to Week 24 will be imputed using a multiple imputation (MI) procedure with a fully conditional specification (FCS) method and predictive mean matching for PEC [64-66]. The use of rescue medication/rescue procedure, reasons for early discontinuation (eg, AE), and duration of study treatment prior to early discontinuation will be captured to address and characterize the nature of

missing data in the MI procedure with an FCS method. Detailed MI model descriptions and analysis procedures will be specified in the SAP.

For analysis of dichotomous endpoints (eg, proportion of subjects with esophageal PEC of < 15 and ≤ 6 eos/hpf at Week 16 and Week 24), all subjects in the FAS will be included in the analyses. Subjects in any of the following cases will be considered as a “non-responder” or “failure”:

- Use of rescue medications/rescue procedures during the Double-Blind Treatment Period;
- Prematurely discontinue from study due to any reason prior to Week 16 and Week 24; or
- With missing data at Week 16 and Week 24 for any reason

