 - ^m Screening EGD (Section 10.3.6) and biopsies (Section 10.3.6.1) should be performed preferably within the first 7 days of the screening period visit to allow sufficient time to confirm histology eligibility. The eosinophil counts from the central reader must be available for confirmation of eligibility. The EREFS will be scored by personnel performing the EGD. If the ET visit is within 4 weeks of the last EGD and biopsy, these procedures do not need to be repeated.
 - ⁿ PK blood samples are to be collected predose (for trough level, within 60-minute period prior to dosing) and 4 hours (± 15 minutes) postdose on Week 0/Day 1 (after 12-lead ECG), and predose on all other indicated days. A PK sample should be taken, if possible, at the time of any SAE or AE leading to study treatment discontinuation. For all PK blood draws, the time of the last dose should be documented.

CCI

- ^p Study drug may be dispensed by secure mail per country specific guidance. Alternatively, a future supply of study medications may be dispensed to the subject at a site visit to cover study medications to be dispensed at the Telehealth Visit.
- ^q Study treatment should be dispensed at Week 24 if the subject continues treatment in the Extension Treatment Period. Additionally, subjects who continue on study but do not enter the Extension Treatment Period on the same day as the Week 24 visit may also be dispensed bridging study treatment.
- ^r At each site visit, previously dispensed medication bottles and any remaining tablets will be collected and counted by the Investigator or qualified staff. The number of remaining tablets in the bottle may be counted by visual inspection via videoconferencing for virtual assessment. The bottle(s) and any remaining tablets must be returned to the site at the next site visit.
- ^s On study visit days with blood draws, subjects should take their dose of study treatment after predose assessments and procedures have been completed.
- ^t The visit window is 14 days following Week 24 visit.

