2.4. ESTIMANDS

The primary and secondary estimands to support regulatory decisions are described in Table 1 below. Supplementary analyses for the primary and secondary estimands will be performed in the Modified Full Analysis Set (mFAS), Completers, and Per Protocol Set, respectively.

List of Estimands

Estimand	Definition	Attributes			
		Population	Variable/ Endpoint	Intercurrent event handling strategy	Population-level summary measure
Primary Estimand	Efficacy of etrasimod on esophageal peak eosinophil count (PEC) at Week 16	Full Analysis Set	Percentage change from Baseline in esophageal PEC at Week 16	Subjects with missing data for any reason (including early discontinuation) or who initiated rescue medication and/or rescue procedure before the primary efficacy assessments prior to Week 16 will have subsequent PEC data set to missing from that point forward through Week 24. The missing data at Week 16 will be imputed using a multiple imputation (MI) method.	Differences between etrasimod (2 mg, 1 mg and any dose) and placebo in percent change from Baseline in esophageal PEC at Week 16

Key Secondary Estimand 1	Efficacy of etrasimod on Dysphagia Symptom Questionnaire (DSQ) at Week 16	Full Analysis Set	Change from Baseline in DSQ at Week 16	Same as the intercurrent event handling strategy for the primary estimand	Differences between etrasimod (2 mg, 1 mg and any dose) and placebo in change from Baseline in DSQ at Week 16
Key Secondary Estimand 2	Efficacy of etrasimod on esophageal PEC at Week 16	Full Analysis Set	Change from Baseline in esophageal PEC at Week 16	Same as the intercurrent event handling strategy for the primary estimand	Difference between etrasimod (2 mg, 1 mg and any dose) and placebo in change from Baseline in esophageal PEC at Week 16
Key Secondary Estimand 3	Efficacy of etrasimod on esophageal PEC at Week 16	Full Analysis Set	Proportion of subjects with esophageal PEC < 15 eos/hpf at Week 16	Subjects in any of the following cases will be treated as nonresponders: use of rescue medication and/or rescue procedure prior to Week 16; premature discontinuation for study due to any reason prior to Week 16; or with missing data at Week 16 for any reason. If subject had rescue medication and/or rescue procedure after Week 16, any assessment after the rescue medication and/or rescue procedure time will be set to missing.	Difference between etrasimod (2 mg, 1 mg and any dose) and placebo in the proportion of responders at Week 16

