6.4. WINDOWING CONVENTIONS

All scheduled study visits are defined relative to Study Day 1, the date of first dose. Scheduled visit windows are defined in Appendix 1 of the protocol. A windowing convention will be used to determine the analysis visit value for a given measurement and will be applicable for all by-visit summaries and analyses for efficacy and safety data. See Table 3 below for specific visit windows.

Visit Windows for Efficacy and Safety Analyses

For all efficacy (except for DSQ total score), CCI health-related quality of life, safety labs and vital signs.	
Scheduled Study Visit (Protocol Scheduled Day)	Analysis Visit Window (Study Day)
Baseline (Double-Blind Treatment Period)	≤ 1 , in addition to Study Day ≤ 1 , a measurement also needs to fulfill the baseline criteria identified in Section 6.2 in order to be considered as baseline measurement
Week 0 (Day 1)	1
Week 2 (Day 15 \pm 3)	2 to 22
Week 4 (Day 29 \pm 3)	23 to 43
Week 8 (Day 57 \pm 5)	44 to 71
Week 12 (Day 85 \pm 5)	72 to 99
Week 16 (Day 113 \pm 5)	100 to 127
Week 20 (Day 141 \pm 5)	128 to 155
Week 24 (Day 169 \pm 5)	156 to 183
Week 28 (Day 197 \pm 7)	184 to 211
Week 32 (Day 225 \pm 7)	212 to 274
Week 46 (Day 323 \pm 7)	275 to 344
Week 52 (Day 365 \pm 7)	> 344

DSQ total score will be calculated every 2 weeks (week 0, 2, 4, 6, 8, 10, etc.) based on the scheduled study day starting on Day 1 For example, DSQ total score for Week 2, 4 and 6 will be calculated on Day 15, 29 and 43, respectively. .

For ECGs, OCT, and PFT.

Scheduled Study Visit (Protocol Scheduled Day)	Analysis Visit Window (Study Day)
Baseline (Double-Blind Treatment Period)	≤ 1
Week 0 (Day 1)	1
Week 24 (Day 169 ± 5)	71 to 267
Week 52 (Day 365 ± 7)	> 267

Windowing will be applied prior to any missing data calculations. The measurement that meets the Baseline criteria described in Section 6.2 will be labeled as “Baseline”. Unscheduled or Screening visits that occurred before the Baseline visit will not be assigned an analysis visit. The early discontinuation visit will be eligible for allocation to an analysis visit. The 2- and 4-Week Follow-Up visits will not be included in the visit windows and will be summarized separately without any window applied.

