17.2.3. PRIMARY ANALYSIS OF SECONDARY EFFICACY VARIABLES

17.2.3.1. Change from Baseline in DSQ total score and Esophageal PEC at Week 16

Analysis of the secondary efficacy variables change from Baseline in DSQ total score at Week 16 will use a linear mixed effect model. The linear mixed effect model will include treatment group, visit, interaction of treatment-by-visit, Baseline history of esophageal dilation (Yes or No), and concurrent PPI therapy (Yes or No) as factors and Baseline DSQ total score as a covariate using an unstructured covariance matrix. If there is a convergence issue in fitting the unstructured covariance, a compound symmetry covariance structure will be used. The Kenward-Rogers method will be used to estimate the denominator degrees of freedom. Change from Baseline in Esophageal PEC at Week 16 will use an ANCOVA model including treatment group and randomization stratification factors as factors and Baseline eosinophil PEC as a covariate. Eosinophil PEC assessments after rescue medication and/or rescue procedure use will be set to missing. LS means at visit and LS mean differences between treatment groups (i.e. etrasimod 1 mg vs placebo, etrasimod 2 mg vs placebo, and etrasimod pooled vs placebo) with p-values and corresponding 95% CIs will be reported. For the individual etrasimod summaries, treatment group will include placebo, etrasimod 1 mg and etrasimod 2 mg. For the pooled etrasimod summary, treatment group will include placebo and pooled etrasimod.

17.2.3.2. Proportion of Subjects with Esophageal PEC < 15 and ≤ 6 eos/hpf at Week 16

Analysis of the secondary efficacy variables proportion subjects with esophageal PEC < 15 eos/hpf at Week 16 and proportion of subjects with esophageal PEC ≤ 6 eos/hpf at Week 16 will be performed for randomization stratification factors of baseline history of esophageal dilation (Yes or No) and concurrent PPI therapy (Yes or No). Subjects who use rescue medication or have a rescue dilation, or with missing data at Week 16 for any reason will be considered nonresponders. The stratified analyses will be performed for randomization stratification factors. Results will be expressed as the number and percentage of subjects who achieved the goal, risk difference in

CCI [REDACTED]

- | [REDACTED]
- | [REDACTED]
- | [REDACTED]
- | [REDACTED]
- | [REDACTED]
- | [REDACTED]
- | [REDACTED]

CCI [REDACTED]

[REDACTED]

CCI [REDACTED]

CCI [REDACTED]	[REDACTED]	[REDACTED]	[REDACTED]	[REDACTED]

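### For a subject who leaves before Week 16 but has an exit biopsy in the Week 16 window, the responder rules conflict and the continuous PEC rule is ambiguous

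*SAP*

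**What the plan says.** **How an exit biopsy becomes a Week 16 value.** Protocol 9.6 says "The ET Visit should occur within 7 days of last dose and before initiation of any new treatments", and asks sites to obtain an EGD where possible if none was done in the preceding 4 weeks. SAP 6.4 sets the Week 16 window at Days 100-127 and adds: "The early discontinuation visit will be eligible for allocation to an analysis visit". SAP 6.3 and 17.1.2 apply windowing before any missing-data rule.

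**Responder endpoints (PEC <15 and ≤6 eos/hpf).**
- Protocol 11.4.1 lists three separate routes to nonresponse: rescue, missing data, and "Prematurely discontinue from study due to any reason prior to Week 16 and Week 24".
- SAP 2.4, key secondary estimand 3 (and 4 by reference), does the same: "premature discontinuation for study due to any reason prior to Week 16".
- SAP 17.2.3.2 makes nonresponders of "Subjects who use rescue medication or have a rescue dilation, or with missing data at Week 16 for any reason". SAP 17.2.2 and footnote d of the Planned Analyses table likewise name only rescue and missing data. Protocol 11.5 also has only these two triggers in its responder paragraph.

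**Continuous PEC endpoints.**
- Protocol 11.4.1: "PEC after rescue medication/rescue procedure use will be set to missing". SAP 8.3 and footnotes c and e say the same, and the footnote to the estimand table lists only rescue as an intercurrent event.
- SAP 17.1.2 opens with three scenarios that give a missing outcome in all efficacy endpoints at subsequent timepoints. The first is "Subjects who 1) discontinue the study for worsening of disease, lack of efficacy, or adverse event related to EoE". Its later sentence on censoring values already collected covers only the two rescue scenarios.
- The primary estimand in SAP 2.4 mentions early discontinuation, in brackets, in the sentence that sets later PEC to missing.

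SAP 3.3 declares no change from the protocol. No section says which rule takes precedence.

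**The concern.** A subject with no rescue and an ET biopsy on, say, Day 105 has an observed PEC that the windowing rule assigns to Week 16. A programmer working from SAP 17.2.3.2 would score it against the threshold; one working from SAP 2.4 would enter a failure. Both would be following approved text. If the count is below threshold, a subject whom the estimand defines as a failure is reported as a responder.

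For percent and absolute change in PEC, the question is whether that value is used or replaced by multiple imputation. Protocol 11.4.1 and 11.5 promise an imputation model that reflects the reason for dropout. SAP 17.1.3 specifies separate models by arm with the stratification variables and does not mention the reason. A blanked value would therefore be imputed largely from subjects who stayed.

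SAP 17.1.3 also allows changes to the missing-data approach after unblinding, reported in the CSR. A rule left open now could end up being settled with treatment codes known.

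**Working it through.** **1. Trace of one subject: no rescue, left the study before Week 16, ET biopsy on Day 105, PEC observed.**

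| Endpoint | Rule | Left for a non-EoE reason | Left for worsening, lack of efficacy or EoE-related AE |
|---|---|---|---|
| Responder | Protocol 11.4.1, SAP 2.4 | Nonresponse | Nonresponse |
| Responder | SAP 17.2.2, 17.2.3.2, footnote d | Scored as observed | Scored as observed, unless 17.1.2 first makes it missing |
| Continuous | Protocol 11.4.1, SAP 8.3, footnotes c and e | Used | Used |
| Continuous | SAP 17.1.2, scenario 1 | Used | Imputed if the ET biopsy counts as subsequent; otherwise used |
| Continuous | SAP 2.4, broad reading | Imputed if subsequent | Imputed if subsequent |

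The responder rows differ whatever the meaning of *subsequent*. The continuous rows differ only through that word and through how SAP 2.4 is read.

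**2. Is the ET biopsy the only candidate for Week 16?** Protocol Appendix 1 says "If the ET visit is within 4 weeks of the last EGD and biopsy, these procedures do not need to be repeated". A Week 16 EGD on Days 108-118 (113 ± 5) therefore removes the need for an ET EGD until Days 136-146 (adding 28). An ET biopsy in Days 100-127 belongs essentially to subjects without a Week 16 EGD, so the rule decides their Week 16 result.

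**3. How many subjects?** The documents give no dropout rate. Assume 10-20% leave before Week 16 (Day 113), with last doses spread evenly over Days 1-112.
- With the ET visit up to 7 days after last dose, a last dose on Days 93-112 can put the biopsy in the window: 20/112 = 17.9%. This is an upper bound.
- If the ET visit falls evenly on days 0-7 after last dose, Days 100-112 contribute 13 and Days 93-99 contribute (1+2+…+7)/8 = 3.5, so (13 + 3.5)/112 = 14.7%.
- All arms, upper bound: 96 × 0.10 × 0.179 = 1.7 and 96 × 0.20 × 0.179 = 3.4.
- 2 mg plus placebo (36 + 24 = 60 under 3:3:2): 60 × 0.10 × 0.179 = 1.1 and 60 × 0.20 × 0.179 = 2.1.

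**4. Effect on responder rates.** One reclassified subject is 1/36 = 2.8 points on an etrasimod arm or 1/24 = 4.2 points on placebo. As an illustration, take assumed counts of 12/36 against 2/24 and an unstratified chi-square test without continuity correction:

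| Etrasimod responders reclassified | Etrasimod vs placebo | p |
|---|---|---|
| 0 | 12/36 vs 2/24 | 0.025 |
| 1 | 11/36 vs 2/24 | 0.041 |
| 2 | 10/36 vs 2/24 | 0.065 |

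**5. Effect on the primary analysis.** Simulation with assumed mean percent change of -60 on active and -15 on placebo (SD 40), and dropouts from a normal distribution with mean 5 and SD 30; 36 vs 24 subjects, compared on ranks without covariates, 1,500 runs. The columns give power when the dropouts' PEC is used and when it is blanked and imputed.

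| Affected dropouts (active, placebo) | Used | Imputed |
|---|---|---|
| 1, 1 | 0.973 | 0.976 |
| 2, 1 | 0.968 | 0.975 |
| 0, 2 | 0.990 | 0.976 |

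The change is small, and its direction depends on which arm loses the subjects.

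**The case against.** For continuous PEC, one reading fits nearly all the text: blank only after rescue. Protocol 11.4.1, SAP 8.3 and footnotes c and e say so. Within SAP 17.1.2, the sentence about values actually collected is confined to rescue, and the exit biopsy is not clearly subsequent to discontinuation. In SAP 2.4 the bracketed mention of discontinuation can be read as a cause of missing data and not as an instruction to blank an observed value.

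This largely stands. A reader might infer that the SAP discards the poor PEC of lack-of-efficacy dropouts and so flatters the arm that loses more of them, or that the primary endpoint is undefined for all early stoppers. The documents do not support either. They leave it open whether the exit biopsy is covered, and the question arises only for ET biopsies in the Week 16 window.

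Nor is it a contradiction to use a value for percent change while scoring the same subject as a nonresponder; that is an ordinary difference between endpoint types. The two size effects also come from different subjects: a PEC shift in the favorable direction needs dropouts with high counts, while a responder reclassification needs dropouts below threshold.

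Planned tipping-point, observed-data, completer, per-protocol and imputation-based responder analyses give partial cover, and this Phase 2 trial reports unadjusted p-values. They vary the assumptions or the population but do not settle the main scoring rule.

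On responders, one can say that SAP 17.2.2 and 17.2.3.2 merely omit a trigger and that the estimand should govern. That is a sensible resolution, but no text states it. The omission also appears in protocol 11.5, so the SAP cannot simply be called a departure from the protocol. One limit applies: SAP 17.2.3.2 runs into a redaction, and SAP 17.2.4 and 17.2.5 are not visible.

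**Conclusion.** The point holds in two parts of unequal strength. For the two responder endpoints the conflict is clear: any-reason study discontinuation before Week 16 is a separate failure criterion in protocol 11.4.1 and SAP 2.4, and absent from the SAP sections that specify the analysis. For continuous PEC there is an ambiguity, because SAP 17.1.2 does not say whether an exit biopsy is subsequent to discontinuation, and neither document fixes the discontinuation date (last dose or ET visit).

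The size is modest. The count of at most about 2-3 of 96 rests on the assumed 10-20% dropout and evenly spread stop dates, and it is lower if ET biopsies are early or not obtained. A responder comparison near the 0.05 level could change on one or two subjects; the rank-based primary result is unlikely to. Severity is minor to moderate.

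**What to change.** Before the double-blind codes are opened:

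1. In SAP 17.2.2, 17.2.3.2 and footnote d, add study discontinuation for any reason before Week 16 as a nonresponse criterion, matching protocol 11.4.1 and SAP 2.4. Record in SAP 3.3 that this list also governs the shorter one in protocol 11.5.
2. In SAP 17.1.2 and the primary estimand in SAP 2.4, state that an observed PEC in the Week 16 window is used unless it follows rescue, matching protocol 11.4.1.
3. Define the date that anchors discontinuation (last dose or ET visit), and say how *prior to Week 16* applies to an ET biopsy taken after Day 113 but inside the window.

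The cost is SAP wording and one derivation flag. No new data are needed.
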